Exclusion criteria:	
 1. Type 1 diabetes or diabetes clearly identified as having monogenetic etiology (e.g.: MODY). 2. Steroid-induced diabetes if steroid use is on-going or most recently taken within the last 3 months. 3. Pregnancy, plans to become pregnant within 6 months, or breast-feeding 4. Any use of insulin in the previous year. 5. Current or previous use of isCGM or rtCGM. 6. Cognitive dysfunction (SPMSQ score ≥ 5). 7. Symptoms of acute metabolic decompensation (extreme thirst, high urinary output, and weight loss, accompanied by acute fatigue or dyspnea). 8. Any terminal condition that would limit life expectancy to < 1 year. 9. Inability or refusal to use isCGM (e.g.: afraid of the device). 10. Inability or refusal to be reached by telephone. 11. Concurrent participation in another diabetes-related trial. 12. Has not already received two doses of a Health Canada-approved vaccine against SARS-CoV-2.
Evaluation criteria	
Primary Outcome: Change in glycated hemoglobin (HbA1c) at 3 months compared to baseline.
 
Secondary Outcomes: Feasibility of recruitment Blood pressure, body weight, waist circumference, and patient-reported outcomes, measured as change in continuous score at 3 months compared to baseline on validated instruments of:
 
 • Diabetes treatment satisfaction • Diabetes self-management empowerment • Diabetes-related distress • Diet • Physical activity

	Safety Outcomes: Any reported adverse events, major adverse events – hospitalization or ED visits. isCGM-related reactions (e.g.: skin reactions).
Treatment	Following informed consent, eligible adults will be randomly allocated to isCGM + education and feedback with a certified diabetes educator (CDE) or enhanced usual care with education and feedback using a 1:1 allocation ratio. The intervention (isCGM or enhanced usual care) will last 6-8 weeks. Those in the isCGM arm are free during the intervention or afterwards to obtain or fund their own supplemental isCGM sensors.
Randomization	Patients will be randomly assigned using a REDCAP based randomization system using variable block size. The computer-generated allocation table would be generated in a formal and secure manner.

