4. STUDY OBJECTIVES

Primary Objective

To evaluate the effectiveness of isCGM with CDE education and feedback on glycemic control at 12 weeks, in adults with type 2 diabetes and uncontrolled HbAc ($> 7.0\%$) not on insulin therapy.

Secondary Objectives

To determine the feasibility of recruiting adults with diabetes in Edmonton-area to a trial of glucose self-monitoring and education.

To determine the effectiveness of isCGM with CDE education and feedback on patient self-management of diabetes, measured using patient reported instruments for diabetes-related quality of life, diabetes treatment satisfaction, diabetes self-management empowerment, diet, and physical activity – at 6 weeks and at 12 weeks.

To determine the safety of isCGM with CDE education and feedback with respect to emergency department visits or hospitalizations, and isCGM-specific reactions (e.g.: skin reactions).

To understand the reasons *why* or *how* isCGM with CDE education is effective or ineffective from the perspective of involved participants and their providers.

To evaluate the effectiveness of isCGM with CDE education and feedback on glycemic control at 24-52 weeks (post-trial observational follow-up).

5. isCGM (INTERMITTENTLY SCANNED CONTINUOUS GLUCOSE MONITOR) – DESCRIPTION OF TECHNOLOGY

Technology – The only isCGM on the market at this time is the FreeStyle Libre 2 system produced by Abbott. FreeStyle Libre 2 sensors use a subcutaneous, wired enzyme glucose-

sensing technology, factory-calibrated to detect glucose levels in *interstitial* fluid by way of a thin filament implanted under the skin. The sensors are water-proof, affix to the skin by medical adhesive, last 14 days each, and are roughly the size of two stacked quarters. They measure interstitial glucose every minute, with readings stored in 15-minute intervals. Patients can scan sensors on-demand, using either a near-field communication-enabled smart phone or the FreeStyle Libre 2 Reader, to receive a glucose result along with historic results for the preceding 8 hours. The FreeStyle Libre 2 system is fully marketed in Canada; in 2020, it's predecessor, the similar FreeStyle Libre flash glucose monitoring system, had over 2 million users internationally.³²

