14. STATISTICAL AND ANALYTICAL METHODS

Our sample size calculation was intended to detect an HbA1c difference of 0.5%, presuming a standard deviation of HbA1c values at 3 months of 0.78% based on a recent similar trial of capillary blood glucose monitoring. To have 80% power to detect this HbA1c difference at a type 1 error rate of 5%, we would need 40 trial-completers in each arm. Given expected loss-to-follow-up rates of 20% or more, our enrollment target will be 100 participants.

Data will be analyzed according to intention-to-treat principles. Patients will be kept in the study group to which they were randomized, and efforts will be taken to ascertain outcome events in all patients randomized. Discontinuation of study treatment (isCGM) or no-show to CDE encounters are not equivalent to withdrawal from the study, and efforts will be made to contact study participants for HbA1c measurements and patient-reported outcomes at 12 weeks regardless.

Outcomes (HbA1c and patient-reported outcomes) are continuous scores – the difference at 12 weeks from baseline will be presented using simple means and standard deviations. On change in HbA1c, our primary outcome, we will test for a difference between intervention and enhanced usual care arms using linear regression with adjustment for age and sex. Secondary outcomes and diabetes-related distress will be analyzed in similar fashion, including follow-up values for patient-reported outcomes obtained at 6 and 12 weeks. Safety outcomes are dichotomous (e.g.: ED visits), and differences between trial arms will be assessed using Fisher's exact test. The primary outcome will be considered statistically significant at $p < 0.05$. Secondary and safety outcomes are considered hypothesis-generating and will also be considered statistically significant at $p < 0.05$. No correction for multiple comparisons is planned *a priori*. If the primary outcome is statistically significant at $p < 0.05$, the Benjamini-Hochberg procedure will be performed on secondary outcomes targeting a false discover rate of 20%, if requested by reviewers.

Secondary analyses are planned, and include:

- Post-hoc analysis of outcomes in clinically relevant groups, e.g.: by sex, baseline self-management empowerment, etc., using the above methods.

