- Partitioning participants into those who improved their HbA1c by 0.5% or more, and examining predictors of improvement using logistic regression with simultaneous incorporation of other explanatory variables.

For the post-trial cohort study, the relationship between outcomes (HbA1c and health care utilization) and study allocation will be examined using linear (log-transformed or untransformed) and logistic regression models with simultaneous adjustment for multiple other variables, selected using a mixed purposeful / stepwise method.

For the qualitative sub-study, semi-structured interviews will be transcribed verbatim, anonymized, and will undergo thematic analysis using constant comparative methods. Co-investigators will interview transcripts independently and meet to develop a coding manual. The qualitative research associate will then code the remaining transcripts line by line. Team members will meet periodically to review and refine codes using a constant comparison method, with further sampling guided by emerging themes until content saturation is achieved.

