- *Limited trial period of 12 weeks.* There is the possibility that insufficient time may have elapsed by the 12 week study HbA1c to see the effect of the intervention, since the 12 week HbA1c may be influenced by blood glucose exposure early in the trial period, before isCGM-based changes are made. Additionally, the 12 month outcome will not be able to speak to the sustainability of any isCGM benefits detected. We have designed a post-trial observational follow-up to address the longer term outcomes of episodic isCGM, recognizing that the follow analysis will no longer benefit from the expected confounder balance of randomization, as participants who consent to data linkage and who have HbA1c measurements post-trial will represent a non-random subset of those initially randomized.
- *Limited support to titrate anti-hyperglycemic medications.* The presumptive mechanism for any improvement in glycemic control is improved diet and lifestyle modification in adults randomized to isCGM. An alternative mechanism may be more rapid medication titration based on isCGM data, instead of HbA1c measurements, which are recommended at intervals no less than 90 days. While the

CDE algorithm (currently under development) may have a role for CDE-to-provider suggestions for medication changes, the intervention is not intended to provide further support or practice change related to provider prescribing (e.g.: decision support, alternate prescribers, provider training).

- *Sample size still has a 20% risk of type 2 error* – Our study is powered to detect a 0.5% difference in HbA1c at a power of 80%. The type 2 error rate (failure to detect a difference on such a difference truly exists) is still 20%, though may be slightly lower if loss-to-follow-up is minimized and recruitment approaches the full 100 participants.

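### The 24- and 52-week HbA1c comparison can use only participants with a later lab value, and section 14 gives week-12 HbA1c no stated role in handling those without one

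*Combined protocol and SAP*

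**What the plan says.** - **Objective.** Section 4 lists among the secondary objectives: "To evaluate the effectiveness of isCGM with CDE education and feedback on glycemic control at 24-52 weeks". It labels this as observational follow-up after the trial.
- **Source of the late values.** Sections 6 and 10 take HbA1c at 24 and 52 weeks from NetCare. No study test is scheduled. Section 10 sends reminder letters to all participants and their providers. The lab nearest to week 52 is used, from data up to week 64; no window is given for week 24.
- **Analysis.** Section 14 covers this in one sentence, which begins "For the post-trial cohort study, the relationship between outcomes (HbA1c and health care utilization) and study allocation". It names linear and logistic regression with covariates that are not listed and are picked by a part-purposeful, part-stepwise procedure. It gives no imputation, weighting, repeated-measures model or missing-data sensitivity analysis.
- **Limitation.** Section 17 says the late analysis loses the balance of randomization because "participants who consent to data linkage and who have HbA1c measurements post-trial will represent a non-random subset of those initially randomized".
- **Week 12.** Section 14 seeks a week-12 HbA1c from everyone randomized, including people who stop the sensor or miss educator sessions. It does not say how that value enters the late analysis.

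**The concern.** A regression of the 24- or 52-week value on allocation drops everyone without a late lab. Whether a patient has a routine HbA1c plausibly depends on how they were doing at week 12. Since allocation may have changed the week-12 value, selection on it is selection on something affected by treatment. Adjusting for baseline factors reduces that bias but does not in general remove it.

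The trial is open-label, so the testing pattern may also differ by arm, for example if one group or its providers react differently to a high reading.

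There is a second hazard. Week-12 HbA1c is likely to be a strong predictor of later HbA1c, so a stepwise search may well select it. As a plain covariate it absorbs the effect already achieved by week 12, and the allocation coefficient becomes the further change after week 12. That is a different quantity from the one in section 4.

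What is at stake is the plan's only evidence on whether any benefit lasts.

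**Working it through.** **1. The plan's own figure.** Section 14: "Our sample size calculation was intended to detect an HbA1c difference of 0.5" percentage points, "presuming a standard deviation of HbA1c values at 3 months of 0.78" percentage points. "To have 80% power to detect this HbA1c difference at a type 1 error rate of 5%, we would need 40 trial-completers in each arm". Allocation is 1:1; two-sided testing is assumed because the plan does not state it.

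n per arm = 2 × (1.960 + 0.842)² × 0.78² / 0.5² = 2 × 7.849 × 0.6084 / 0.25 = 38.2, so 39 by the normal approximation. With the t distribution, power is 79.8% at 39 and 80.8% at 40, so 40 is reproduced. Enrolment at 20% loss is 80 / 0.80 = 100, also reproduced. The plan gives no power or expected testing rate for the late comparison.

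**2. Bias from using only those with a late lab.** The documents supply no testing rate and no correlation between visits, so these inputs are assumptions: SD 0.9, correlation 0.7 between weeks 12 and 52, true arm difference -0.5 at week 12 and -0.30 at week 52, base testing probability 0.6, and log-odds of having a lab linear in week-12 HbA1c (slope per 1 point). Large-sample simulation, unadjusted difference among those tested; ranges are over repeat runs:

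| Testing depends on week-12 HbA1c | Late labs only | Bias | Using week 12 |
|---|---|---|---|
| Both arms, slope 0.5 | -0.29 to -0.28 | 0.01-0.02 | about -0.30 |
| Both arms, slope 1.0 | -0.25 | 0.05 | about -0.30 |
| Both arms, slope 1.5 | -0.21 | 0.09 | about -0.30 |
| isCGM arm only | -0.07 to -0.05 | 0.23-0.25 | about -0.30 |
| Control arm only | -0.50 to -0.48 | 0.18-0.20 | about -0.30 |

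The last column predicts the late value from week-12 HbA1c within arm and averages over everyone with a week-12 value. It stands in for multiple imputation or a likelihood-based repeated-measures model.

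**3. The same check at the protocol's SD of 0.78** (correlation 0.7, true -0.30, slopes per SD). Common slopes of 0.5 and 1 give -0.283 and -0.241. Opposite slopes of 0.5 in the two arms give -0.072 or -0.489. The week-12-informed estimate stays at -0.30.

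**4. With baseline HbA1c as a covariate.** This is an assumption, since the covariates are unnamed: correlation of baseline with week 12 of 0.5-0.7 and with week 52 of 0.4-0.6, SD 0.78, slope 1 per point. Common selection gives -0.27 to -0.28, a bias of 0.02-0.03. Selection in the isCGM arm only gives about -0.15 to -0.22, a bias of 0.08-0.15. Selection in controls only reaches about -0.41, a bias of 0.11.

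**5. Week-12 HbA1c as a plain covariate.** With equal SDs the allocation coefficient is Δ52 - ρ × Δ12 = -0.30 - 0.7 × (-0.50) = +0.05. A true benefit of 0.30 would appear as none.

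**6. Testing that also depends on the unseen late value.** With SD 0.78, correlation 0.7 and a true -0.50 at both times, the week-12-informed estimate is -0.485 to -0.434, against -0.472 to -0.370 for late labs only. Bias falls but remains.

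**The case against.** The plan is candid. It calls this follow-up observational, says the balance of randomization is lost, and sends reminders to all participants and providers. Section 14 treats secondary outcomes as hypothesis-generating. All of that stands. It bears on how firmly the result may be read, but reminders do not make testing random, and the objective remains an arm effect.

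The unadjusted figures overstate what an adjusted regression would show. This stands too: baseline adjustment narrows the bias, as step 4 shows. With 50 per arm and a common slope of 1, a bias of 0.05 sits beside a sampling SD of 0.234. Root mean squared error is √(0.05² + 0.234²) = 0.24, against 0.23 for the week-12-informed analysis. In that case the practical gain is small. The larger distortions need an arm-specific testing pattern, for which the documents give no evidence either way.

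A reader might infer that the plan excludes week-12 HbA1c. It does not: the covariates are unnamed, so its role is unspecified. A reader might also infer that using week 12 would fully correct the estimate. That holds only if testing depends on observed data. Late data could be recovered from week 12 only for those who have that value, and the synopsis expects 20-30% loss to follow-up. Refusal of data linkage, which section 17 also names, need not be explained by HbA1c at all.

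**Conclusion.** The concern holds in limited form. The late comparison can use only people with a later lab, the plan itself calls them a non-random subset, and it names no method for the rest. The best available predictor is collected but given no stated role, and stepwise selection could bring it in where it does harm.

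If testing depends on week-12 HbA1c, the bias on a true -0.30 is modest under a pattern common to both arms: about 0.01-0.09 points unadjusted, less with baseline adjustment. It is about 0.1-0.25 if the pattern differs by arm, with baseline-adjusted values toward the lower end. These sizes depend on assumed correlations, testing rates and effects, so they show what is possible and are not estimates for this trial.

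It would be tempting to call the long-term objective unanswerable. The documents do not support that: the common-pattern bias is small, and the direction and size of any arm-specific pattern are unknown. The primary 12-week comparison is not touched.

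**What to change.** In section 14, for HbA1c at 24 and 52 weeks:

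- Replace the stepwise regression with one mixed model of HbA1c at weeks 12, 24 and 52: arm, visit, arm-by-visit, baseline HbA1c-by-visit, age and sex, with unstructured covariance. Include everyone randomized who has at least one post-baseline HbA1c. Multiple imputation using arm, baseline and week-12 HbA1c would serve equally.
- State that week-12 HbA1c will not be entered as an ordinary covariate.
- Report the number and proportion with a late lab, by arm and time point.
- Keep the regression on late labs only as a sensitivity analysis, and add one for testing that depends on the unseen late value, such as a shift applied to imputed values over a stated range.

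The cost is analysis-plan wording; no new data are needed. The downsides should be stated. The model assumes testing depends on observed HbA1c, so it reduces bias without guaranteeing its removal. It does not address refusal of data linkage. It treats the nearest available lab as if taken at a fixed visit.

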Sample size	A target sample of 100 patients was chosen based on funding constraints, power / sample size considerations, and expected loss to follow-up of 20-30%. The minimum number of trial completers required to have 80% power to detect an HbA1c difference of 0.5% is 80.
Follow-up	Follow-up (week 5-6) CDE virtual education and feed-back session. 12-week bloodwork encounter at outpatient lab. 12-week in-person study encounter to complete study measurements. After conclusion of the 12 week trial period: Post-trial qualitative interviews with select consenting participants. Post-trial administrative linkage to examine outcomes at 24-52 weeks from randomization – no direct participant involvement.

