10. STUDY OUTCOMES AND VARIABLES

Case report forms are provided in Appendix 5. These will be translated into electronic documents to be completed by participants via a password protected webportal (EpiCore).

Primary Outcome:

- Change in HbA1c at 12 weeks compared to baseline.

Secondary Outcomes:

- Feasibility of recruitment
 - Participant referral, screening, and randomization rates over time
 - Reasons for inclusion / exclusion of all participants referred.
- Change in scores at 6 and 12 weeks compared to baseline, on the patient-reported outcomes shown in Table 1, below.
- isCGM participants only – change in time-in-target range, coefficient of variation, and glucose management indicator at 12 weeks compared to baseline.

Table 1: Patient-Reported Outcomes

Outcome	Instrument	Number of items
Diabetes treatment satisfaction – Status score	Diabetes Treatment Satisfaction Questionnaire (DTSQs) ³⁷ (weeks 6 and 12)	8
Diabetes treatment satisfaction – Change score	Diabetes Treatment Satisfaction Questionnaire (DTSQc) (week 6 only)	
Self-management empowerment	Diabetes Empowerment Scale – Short Form (DES-SF) ³⁸ (weeks 6 and 12)	8
Diabetes-related distress	Problem Areas in Diabetes (PAID) Questionnaire ³⁹	20
Diet	UK Diabetes and Diet Questionnaire (UKDDQ) ⁴⁰ (weeks 6 and 12)	25
Physical activity	International Physical Activity Questionnaire (IPAQ) short form ^{41,42} (weeks 6 and 12)	7
Health status	Euroqol EQ-5D-5L (weeks 6 and 12)	5

* In addition to collection at baseline.

Safety outcomes at 12 weeks:

- Any adverse events (serious and non-serious) occurring from baseline to 12 weeks will be identified and tracked at the 12 week study visit by patient interview, and reviewed

by study investigators to determine whether clinically attributable to diabetes, diabetes management, or isCGM. isCGM issues (e.g.: skin reactions) will be specifically sought.

- Emergency department visits or hospital admission for any reason, identified from patient interview and from NetCare review.

Qualitative Outcomes: Semi-structured interviews will undergo thematic analysis using constant comparative methods. The starting point will be the participant and provider experience with isCGM or enhanced usual care, with a particular focus on barriers and enablers of effectiveness (see Appendix 6, interview guides). Semi-structured interviews will take place for participants after trial completion (from 12-24 weeks).

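### Section 17 gives the study 80% power, but the plan's own 20-30% loss from 100 enrolled gives about 75-81%, below 80% once loss passes about 22%

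*Combined protocol and SAP*

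**What the plan says.** Three places bear on this point.

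- **Study Synopsis, Sample size.** The target of 100 reflects funding constraints, power considerations and "expected loss to follow-up of 20-30" per cent. The same row adds: "The minimum number of trial completers required to have 80% power to detect an HbA1c difference of 0.5% is 80".
- **Section 14, Statistical and Analytical Methods.** "To have 80% power to detect this HbA1c difference at a type 1 error rate of 5%, we would need 40 trial-completers in each arm". The calculation rests on "presuming a standard deviation of HbA1c values at 3 months of 0.78" per cent. On enrolment: "Given expected loss-to-follow-up rates of 20% or more, our enrollment target will be 100 participants".
- **Section 17, Feasibility and Limitations, last bullet.** "Our study is powered to detect a 0.5% difference in HbA1c at a power of 80" per cent. No completer count is attached. The type 2 error is put at 20%, "though may be slightly lower if loss-to-follow-up is minimized and recruitment approaches the full 100 participants".

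The primary outcome in Section 10 is "Change in HbA1c at 12 weeks compared to baseline".

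**The concern.** The Synopsis and Section 14 tie 80% power to 80 completers. Section 17 drops that condition and gives 80% as the power of the study. With 100 enrolled, 80 completers is what remains at 20% loss, the most favourable end of the range the plan expects. Any greater loss falls short of the plan's own minimum, yet the only departure Section 17 mentions is an improvement.

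A limitations bullet on type 2 error is where a reader would look for the chance that a null primary result missed a real effect. If loss reaches 30%, that chance is about one in four for a true 0.5% difference, not the one in five stated.

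**Working it through.** **Inputs.** Difference 0.5%, SD 0.78%, type 1 error 5%, 80% power (Section 14); 1:1 allocation, 100 enrolled, 20-30% loss (Synopsis). The plan does not state whether the test is one- or two-sided. Two-sided is assumed because it fits the stated number; a one-sided 5% test would have 88.9% power at 40 per arm (normal approximation).

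**Step 1: reproduce the plan's figure.** Normal approximation:

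n per arm = 2 × SD² × (1.960 + 0.842)² / difference² = 2 × 0.6084 × 7.849 / 0.25 = 38.2, rounded up to 39.

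The two-sample t-test (noncentral t) needs 39.19 per arm, rounded up to 40. The plan's 40 per arm is confirmed. Enrolment: 80 / (1 − 0.20) = 100, also confirmed, but for exactly 20% loss.

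**Step 2: completers the plan expects.** 100 × (1 − 0.20) = 80; 100 × (1 − 0.25) = 75; 100 × (1 − 0.30) = 70.

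**Step 3: power at those numbers.** With n per arm, the noncentrality is 0.5 / (0.78 × √(2/n)) on 2n − 2 degrees of freedom. For n = 35 this is 0.5 / (0.78 × 0.2390) = 2.68 on 68 df.

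| Loss | Completers | Power, t-test | Type 2 error | Power, normal approx. | Difference detectable at 80% power (t-test) |
|---|---|---|---|---|---|
| 0% | 100 | 88.8% | 11.2% | 89.4% | not needed here |
| 20% | 80 | 80.8% | 19.2% | 81.8% | 0.495% |
| 25% | 75 | 78.2% | 21.8% | 79.3% | 0.511% |
| 30% | 70 | 75.3% | 24.7% | 76.5% | 0.530% |

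**Step 4: where power crosses 80%.** By t-test at 2 × 39.19 = 78.4 completers, which is 1 − 78.4/100 = 21.6% loss. By normal approximation at 76.4 completers, or 23.6% loss. By either method most of the 20-30% range lies below 80%.

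**Step 5: does the planned model change this?** Taking 2 degrees of freedom for age and sex, with no variance explained, gives 75.3% at 70 completers and 80.8% at 80. It does not.

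**Step 6: sensitivity to the SD.** The 0.78% is an SD of 3-month values, while the analysed outcome is change. The documents give no SD of change. If the SDs at baseline and 12 weeks are equal and their correlation is r (assumed), the SD of change is 0.78 × √(2(1 − r)).

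| Assumed r | SD of change | Power, 70 completers | Power, 80 completers |
|---|---|---|---|
| 0.3 | 0.923% | 60.8% | 66.7% |
| 0.5 | 0.780% | 75.3% | 80.8% |
| 0.7 | 0.604% | 92.7% | 95.5% |

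The plan's figure therefore carries over to the change score only at a correlation of about 0.5.

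**The case against.** The best defence is that nothing has been miscalculated. Both 40 per arm and 100 enrolled reproduce, and the Synopsis shows the loss range and the 80-completer minimum side by side, so a reader can see that 30% loss leaves too few. To call a study powered at 80% is the usual shorthand for a design target, and the bullet is itself a caveat that links type 2 error to loss and recruitment. The shortfall is small: the difference detectable at 80% power rises only to 0.53%. It also depends on the SD: an SD of change of about 0.74%, some 6% lower than 0.78%, would restore 80% power at 70 completers.

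Much of this stands. The sample size is right, the effect is modest, and the 21.6% crossing should not be read too precisely, since the normal approximation puts it at 23.6%. But what the Synopsis discloses does not correct the unconditional figure in Section 17, and a reader would have to combine two sections and run a power calculation to find the gap. The link to loss is drawn in the favourable direction only, while the plan expects the unfavourable one over most of its range. Uncertainty about the SD works both ways, and is a further reason not to give a single 80%.

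**Conclusion.** The concern holds. On the plan's own inputs, Section 17's 80% power and 20% type 2 error are met only near the favourable end of the expected loss. Over the 20-30% range, power runs from about 81% down to 75% and type 2 error from about 19% up to 25%. The favourable qualifier is genuine, since power with no loss would be 88.8%, but the opposite case is left out. The shortfall is about 5 points at most and does not invalidate the design.

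The result rests on a two-sided 5% test, equal arms, and an SD of change equal to the 0.78% given for 3-month values. The last is an assumption the documents do not support either way; under correlations of 0.3 to 0.7, power at 70-80 completers could lie anywhere from about 61% to 96%. The correction should be made, but it concerns reporting and not conduct.

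**What to change.** Reword the last bullet of Section 17 and put one matching sentence beside the enrolment target in the Synopsis and Section 14. Suggested text:

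> With 100 enrolled and 20-30% loss to follow-up (70-80 completers), power to detect 0.5% is about 75-81% and type 2 error about 19-25%. Type 2 error exceeds 20% if loss exceeds about 22%, and is clearly lower only if loss is below 20%. These figures assume that the 0.78% SD of 3-month values also applies to the analysed change in HbA1c.

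The statements that tie 80% power to 40 completers per arm are correct and can stay. Holding 80 completers at 30% loss would take 80 / 0.70 = 114.3, so 115 enrolled, but funding limits the target and the correction does not require it.

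The cost is one reworded bullet and one sentence in two other places. The stated power becomes a range whose lower end is about 5 points less favourable. Enrolment, the primary test, the decision rule and the budget are unchanged.
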